Section 1, Overall Design, Treatment Arms and Duration	
From: "The two cohorts in Part A may be dosed sequentially (i.e., dosing in Cohort 2 starts after dosing in Cohort 1 is completed) or in an overlapping/interlocking fashion. The exact sequence of dosing will be determined together with the site investigator based on emerging information about the half-life of GSK3036656 in humans and logistical considerations."
 
To: "The two cohorts in Part A will be dosed sequentially (i.e., dosing in Cohort 2 starts after dosing in Cohort 1 is completed). If it is considered desirable to dose Cohorts 1 and 2 in an overlapping/interlocking fashion (for example, if the half-life of GSK3036656/washout period makes sequential dosing impractical), approval for such dosing will be sought from the Regulatory Agency. Dosing in an overlapping/interlocking fashion will only take place if such approval is obtained."
	To address the concern from the MHRA about the possibility of overlapping/interlocking dosing.
Section 4.1, Study Design	
From: The two cohorts in Part A may be dosed sequentially (i.e., dosing in Cohort 2 starts after dosing in Cohort 1 is completed) or in an overlapping/interlocking fashion. The exact sequence of dosing will be determined together with the site investigator based on emerging information about the half-life of GSK3036656 in humans and logistical considerations."
 
To: The two cohorts in Part A will be dosed sequentially (i.e.,
	To address the concern from the MHRA about the possibility of overlapping/interlocking dosing.

Section # and Name	Description of Change	Brief Rationale
	
dosing in Cohort 2 starts after dosing in Cohort 1 is completed). If it is considered desirable to dose Cohorts 1 and 2 in an overlapping/interlocking fashion (for example, if the half-life of GSK3036656/washout period makes sequential dosing impractical), approval for such dosing will be sought from the Regulatory Agency. Dosing in an overlapping/interlocking fashion will only take place if such approval is obtained.”
 
Figure 1, footnote (bullet 3) updated.
 
From: Cohorts may be dosed in an overlapping fashion, the exact sequence of dosing will be determined together with the investigator based on emerging information about the half life of GSK3036656 in humans and logistical consideration
 
To: Cohorts 1 and 2 will be dosed sequentially. If it is considered desirable to dose Cohorts 1 and 2 in an overlapping/interlocking fashion, approval will be sought from the Regulatory Agency first
	
Section 5.1, Inclusion Criteria	
From: “Male subjects with female partners of child bearing potential must comply with the following contraception requirements from the time of first dose of study medication until follow up.”
 
To: “Male subjects with female partners of child bearing potential must comply with the following contraception requirements from the time of first dose of study medication until 90 days after the last dose of study treatment (i.e. one sperm cycle).”
	To allow the completion of one sperm cycle before possible pregnancy.

TABLE OF CONTENTS

	PAGE
PROTOCOL AMENDMENT SUMMARY OF CHANGES TABLE.....	4
1. PROTOCOL SYNOPSIS FOR STUDY [201040].....	9
2. INTRODUCTION.....	13
2.1. Study Rationale	13
2.2. Brief Background	13
3. OBJECTIVE(S) AND ENDPOINT(S).....	14
4. STUDY DESIGN	15
4.1. Part A (Single Dose).....	15
4.1.1. Food Effect.....	16
4.2. Part B (Repeat Dose).....	17
4.3. Type and Number of Subjects.....	18
4.4. Design Justification.....	18
4.5. Dose Justification.....	18
4.6. Benefit:Risk Assessment	20
4.6.1. Risk Assessment	21
4.6.2. Benefit Assessment	24
5. SELECTION OF STUDY POPULATION AND WITHDRAWAL CRITERIA	24
5.1. Inclusion Criteria	24
5.2. Exclusion Criteria.....	26
5.3. Screening/Baseline/Run-in Failures	27
5.4. Individual Withdrawal/Stopping Criteria.....	27
5.4.1. Liver Chemistry Stopping Criteria	28
5.4.1.1. Study Treatment Restart or Rechallenge.....	29
5.4.2. QTc Stopping Criteria	29
5.4.3. Haematology Stopping Criteria	29
5.4.4. Vital Signs Stopping Criteria	29

1. PROTOCOL SYNOPSIS FOR STUDY [201040]

Rationale

This study is the first time into human study (FTIH) for GSK3036656. The study will evaluate the safety, tolerability and pharmacokinetics (PK) of single ascending and repeat oral doses of GSK3036656 in healthy adult volunteers.

The results of this study are intended to be used to identify appropriate and well tolerated doses of GSK3036656 to be used in further studies. A food effect assessment will also be undertaken to investigate the influence of food on the pharmacokinetics of GSK3036656.

Objective(s)/Endpoint(s)

Objectives	Endpoints
Primary	

 • To investigate the safety and tolerability of GSK3036656 after single ascending and repeat oral doses in healthy adult subjects • To determine the pharmacokinetics of single and repeat doses of GSK3036656 in healthy subjects 	
 • Safety and tolerability of GSK3036656: 
 ○ Adverse Events ○ Clinically relevant changes in safety parameters: 12-lead electrocardiogram (ECG), telemetry, vital signs (systolic and diastolic blood pressure, heart rate, temperature), clinical laboratory data (haematology, clinical chemistry, urinalysis) • Derived pharmacokinetic parameters for GSK3036656 including area under the plasma drug concentration versus time curve (AUC(0-t), AUC(0-∞), AUC(0-τ)), maximum observed plasma drug concentration (Cmax), time to maximum observed plasma drug concentration (tmax), and apparent terminal half-life (t1/2) as appropriate
Secondary	

 • To assess the effect of food on the pharmacokinetics of GSK3036656 following an oral dose in healthy subjects • To assess preliminary dose proportionality of GSK3036656 following single and 	
 • Derived pharmacokinetic parameters for GSK3036656 including AUC(0-t), AUC(0-∞), Cmax, tmax, and apparent terminal half-life (t1/2) • AUC(0-t), AUC(0-∞), and Cmax following single dose and AUC(0-τ) and Cmax following repeat dose for the assessment

Objectives	Endpoints

repeat oral doses, as data permit
 
 • To examine the extent of accumulation and achievement of steady-state following repeat oral doses of GSK3036656, as data permit • To define the metabolic profile of GSK3036656 by identifying and quantifying, where possible and appropriate, GSK3036656-related material in plasma and urine following a single and repeated oral administration of GSK3036656 	
of dose proportionality
 
 • Observed accumulation ratio based on AUC(Ro) and Cmax (RCmax) and steady-state ratio (Rss) following repeat dosing • Trough plasma concentrations at the end of the dosing interval (C_T) to assess the achievement of steady-state of GSK3036656 following repeat oral doses • Structure and concentration of GSK3036656-related material in plasma and urine

Overall Design

Treatment Arms and Duration

Part A:

For the single dose part, there will be up to 2 cohorts with up to 4 treatment (dosing) periods in each cohort (including a food effect treatment period). Initially, there will be a 14 day wash out period for individual subjects between each dose level which is considered sufficient in light of the predicted half-life of GSK3036656 [on average, approximately 30 hours (range: 12 to 72 hours) based on the various preclinical extrapolation methods], however this may be revised once relevant PK data is obtained. 9 subjects per cohort will be enrolled and randomised to ensure adequate safety, tolerability and PK information is gained and a balanced randomisation is achieved across all treatment (dosing) periods.

During each treatment (dosing) period, GSK3036656 will be administered to 6 subjects and placebo will be administered to 3 subjects. As this is a FTIH study, each treatment (dosing) period will be staggered over 2 days. On Day 1, one subject will receive GSK3036656 and one subject will receive placebo. The remaining subjects will be dosed one day later provided satisfactory safety and tolerability is demonstrated for the subjects dosed on Day 1. A treatment (dosing) period does not have to be staggered if the dose administered is equal to or lower than a dose that has been already tested and found to be safe and well tolerated.

Subjects will attend the unit on Day -1 for assessments and a meal. The subjects will then fast overnight (at least 8 hours) and be dosed the following morning (Day 1). Dosing with food may also be used in Part A once results from the food effect analysis are available. Dividing the total dose for the treatment (dosing) period into 2 or 3 smaller doses administered within 24 hours may also be done. The decision to divide the total dose into smaller doses will be made by the GSK study team in conjunction with the Principal Investigator. Post-dose, subjects will undergo safety and PK assessments. All subjects will remain in the unit until the 72 hour PK sample has been taken since this will enable a better assessment of their safety and will reduce the risk of subjects not returning for their visits. Subjects will be released at the discretion of the investigator following completion of the assessments provided there are no safety concerns identified from review of the clinical safety data. Approximately 14 days after their last dose, subjects will return to the unit for a follow-up visit.

The starting dose in Part A will be 5 mg. The dose will then be escalated up to a dose (no higher than 1500 mg) at which PK exposures do not exceed predefined limits determined from preclinical safety data (individual AUC[0-24]<4.9 µg.h/ml, individual Cmax<0.443 µg/ml). Dose escalation will only take place provided GSK3036656 is well tolerated and following review of all available safety, tolerability and pharmacokinetic data from the previous treatment (dosing) period by the Dose Escalation Committee.

The two cohorts in Part A will be dosed sequentially (i.e., dosing in Cohort 2 starts after dosing in Cohort 1 is completed). If it is considered desirable to dose Cohorts 1 and 2 in an overlapping/interlocking fashion (for example, if the half-life of GSK3036656/washout period makes sequential dosing impractical), approval for such dosing will be sought from the Regulatory Agency. Dosing in an overlapping/interlocking fashion will only take place if such approval is obtained. In any case, a wash out period of at least 4 half-lives will be required before the same group of subjects is dosed again.

Part A - Food Effect:

An assessment of the effect of food on the exposure to GSK3036656 will be incorporated into the single dose part of the study (Part A). This assessment will be done by administering a single dose of GSK3036656/placebo with a high fat meal provided this dose was well tolerated in a previous treatment (dosing) period in the same cohort when administered in the fasted state. The dose to be administered with food will be selected such that, when administered in the fasted state, it provides exposure no higher than 50% of the highest exposure allowed in the study, in the eventuality that the presence of food unexpectedly enhances absorption.

Part B:

Part B (Cohorts 3, 4, 5, and 6) will comprise up to 4 cohorts of 10 (8 active: 2 placebo) healthy adult subjects to examine the safety, tolerability and PK of a repeated daily dose of GSK3036656 over a period of up to 14 days. Progression to Part B from Part A will be based on an acceptable safety, tolerability and PK profile in Part A. Appropriate doses and dose regimens for Part B will be selected by the Dose Escalation Committee based

on available safety, tolerability and PK data from Part A and/or any preceding repeat dose cohorts from Part B. A decision to proceed to a higher dose in Part B will be based on the review of safety data from at least the first week of dosing and PK data from at least the first 48 hours of dosing at the preceding dose.

On Day –1, subjects will report to the unit for assessments and a meal. The subjects will then fast overnight (at least 8 hours) and be dosed the following morning (Day 1). Dosing with food may also be done if there are PK or tolerability reasons making it preferable to dose in a fed state. Dividing the total daily dose into 2 or 3 smaller doses administered over 24 hours may also be done. The decision to divide the total dose into smaller doses will be made by the GSK study team in conjunction with the Principal Investigator. Post-dose, subjects will undergo safety and PK assessments. Subjects will remain in the unit for at least 72 hours after the initial dosing. If they are released after that, it would be done at the discretion of the investigator following completion of the assessments on Day 4 and provided there are no safety concerns. If released, subjects will then return to the clinical unit each morning to receive their daily dose and assessments for the duration of Part B. Dosing will be scheduled to occur at approximately the same time each day for each individual subject. Subjects will be required to spend at least the last 24 hours at the end of the dosing period in the unit in order to complete the necessary safety assessments and PK sampling. The subjects may then be discharged from the unit but, if discharged, will be required to return for additional PK sampling at 36, 48 and 72 hours post dosing. Approximately 14 days after their last dose, subjects will return to the unit for a follow-up visit.

The total duration of the study for each subject recruited into Part A will be approximately 12 weeks. For subjects recruited into Part B the total study duration will be approximately 8 weeks.

Type and Number of Subjects

Up to 18 subjects (excluding possible replacements) will be recruited into the single ascending dose part of the study and up to 40 subjects (excluding possible replacements) will be recruited for the repeat dose. Both males and females of non child-bearing potential will be included.

Analysis

The focus of this FTIH study, both single and repeat dose phases, is to evaluate the safety, tolerability and pharmacokinetics of GSK3036656. No formal statistical hypotheses will be tested.

Safety analyses

Safety data will be presented in tabular and/or graphical format and summarized descriptively according to GSK's Integrated Data Standards Library (IDSL) standards.

Pharmacokinetic Analyses

From the plasma concentration-time data, the following pharmacokinetic parameters will be determined, as data permit: maximum observed plasma concentration (C_{max}), time to C_{max} (t_{max}), area under the plasma concentration time curve [AUC(0-t), AUC(0- τ), and AUC(0- ∞)], and apparent terminal phase half-life (t_{1/2}). Trough concentration (C_T) samples collected on the specified days may be used to assess attainment of steady state. To estimate the extent of accumulation after repeat dosing, the observed accumulation ratio for AUC (R_o) and C_{max} (R_{Cmax}) may be determined. To estimate the pharmacokinetic linearity, the state ratio (R_{ss}) may be determined. From the urine concentration data, the following pharmacokinetic parameters will be determined, as data permit: urinary excretion of unchanged drug (A_e), fraction of the dose excreted in the urine (f_e), and the renal clearance (C_{Lr}).

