4.5. Dose Justification

Dose selection of GSK3036656 for this FTIH study was based on no observed adverse effect level (NOAEL) data, predicted pharmacokinetics for humans using the pharmacokinetic data from various preclinical species, and a targeted therapeutic exposure based on efficacy data from a murine model of chronic lung infection. GSK3036656 PK parameters and exposure values were converted from whole blood values to plasma values when necessary. GSK3036656 suppresses protein synthesis in *Mycobacterium tuberculosis* by inhibiting the enzyme Leucyl t-RNA synthetase which is not a human target; thus, the minimum anticipated biological effect level (MABEL) in humans for GSK3036656 could not be determined.

The *in vivo* PK parameters obtained in preclinical species (CD-1 mouse, SD rat, and beagle dog) after 1 mg/kg intravenous administration and the *in vitro* parameters (intrinsic Cl from microsomes and hepatocytes, plasma protein binding, and blood to plasma ratio) were used for calculations. The GlaxoSmithKline software package PK Predictor Pro (GUI v1.1.45 Calculation Engine v1.4.4) was used for IVIVE, LBF, GFR and allometric scaling and the CloePK software (Cyprotex) for the physiologically based pharmacokinetic (PBPK) modelling.

Predicted human clearance values ranged from approximately 1.1 (allometric scaling with MLP) to 7.2 (PBPK) mL/min/kg while predicted volume of distribution ranged from 3.5 (PBPK) to 4.5 (simple allometry) L/kg. Preclinically, oral bioavailability ranged from approximately 60% to greater than 100%.

The NOAEL dose in the rat (the most sensitive species) was 30 mg/kg with an average AUC(0-24) and Cmax of 90.5 $\mu\text{g.h/mL}$ and 7.59 $\mu\text{g/mL}$, respectively; the NOAEL dose in the dog was 20 mg/kg with an average AUC(0-24) and Cmax of 147.0 $\mu\text{g.h/mL}$ and 13.3 $\mu\text{g/mL}$, respectively. Due to the presence of heart valvular and vascular lesions in dogs at higher doses, and based on discussions with the GSK Cardiovascular Safety panel, the maximum individual daily human exposure after single or repeat dose in the study will be limited to 4.9 $\mu\text{g.h/mL}$ for AUC(0-24) and 0.443 $\mu\text{g/ml}$ for Cmax (30-fold margins from the dog NOAEL exposures of 147.0 $\mu\text{g.h/mL}$ and 13.3 $\mu\text{g/ml}$, respectively).

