5.5. Dose Escalation Stopping Criteria

Dose escalation in Part A or Part B will be stopped if any of the following occurs in a group/cohort:

1. There is substantially increased incidence and/or severity of clinically significant adverse events or withdrawals possibly related to GSK3036656 in the active treatment subgroup at the last dose level administered as compared to the placebo subgroup. The GSK Study Team in conjunction with the study investigator will determine the significance of the adverse events or withdrawals and make a decision about whether stopping further dose escalation is necessary.
2. At least one subject has a plasma AUC (0-24) higher than 4.9 µg.h/mL or a plasma Cmax higher than 0.443 µg/mL on any day.
3. For Part A, no meaningful increase in exposure is observed with increase in dose (i.e., a plateau in exposures is reached).

Note: If dose escalation is stopped due to reasons 1 or 2 above occurring at the last dose, dosing at a lower level (e.g., an intermediate level between the last dose and a previous dose where dose escalation stopping criteria were not met) could be allowed. The GSK Study Team in conjunction with the study investigator will decide whether dosing at such level could be done and will select the dose to be administered.

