6.3. Planned Dose Escalation and Adjustments

After the initial dose of GSK3036656, the decision to proceed to each subsequent dose level will be made by the Dose Escalation Committee (DEC) based on safety, tolerability and preliminary pharmacokinetic data from the prior lower dose level (Further details regarding dose escalation can be found in the 201040 Dose Escalation Charter). In Part A, safety data for at least 5 days post-dose and PK data for at least 2 days (48 hours) postdose from at least 4 subjects who received active treatment at the prior lower dose level will be reviewed before dose escalation. In Part B, safety data for at least the first 1 week (7 days) of dosing and PK data for at least the first 2 days (48 hours) of dosing from at least 4 subjects who received active treatment at the prior lower dose level will be reviewed before dose escalation. The actual doses to be administered will be selected by the DEC and may involve either an increase or a decrease in the dose, or repeating the same dose.

The exposures (AUC, Cmax) expected with the next selected dose will be predicted by pharmacokinetic assessment and modelling, and by calculating Bayesian predictive probabilities as data permit (more details in Section 10.3.1).

In toxicology studies in dogs, heart valvular and vascular lesions have been observed at relatively high doses and exposures; no such lesions have been seen in rats at similar exposures. To avoid the risk of this adverse event in the FTIH subjects, exposures in the FTIH study will be limited to predefined levels. Based on discussions with the GSK Cardiovascular Safety panel, the study will aim to limit the maximum individual daily plasma AUC(0-24) and Cmax after single or repeat dose to 4.9 µg.h/mL and 0.443 µg/ml, respectively - a 30-fold margin from the corresponding dog NOAEL exposures of 147.0 µg.h/mL and 13.3 µg/ml at which no valvular or vascular lesions have been detected.

Note: The term “mean” applied to group human exposure parameters (e.g., AUC) in this section refers to Geometric Mean of a dose cohort.

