6.3.1. Dose escalation in Part A

In Part A, bigger dose escalation steps may be allowed at lower doses and systemic exposures as the expected risk of adverse events at these exposures is low. At higher doses, smaller dose escalation steps will be used to minimize the risk of adverse events and gastrointestinal intolerance.

The following rules will guide dose selection in Part A:

1. No dose escalation to the next dose will be higher than 6-fold.
2. Once the dose is ≥ 300 mg, any further dose escalation will be no higher than 3-fold irrespective of the observed exposures.
3. The highest dose in Part A will not exceed 1500 mg.
4. A proposed dose will be acceptable if the predicted probability of an individual exceeding a Day 1 plasma AUC (0-24) of 4.9 µg.h/mL or Cmax of 0.443 µg/mL, as estimated by PK modeling and Bayesian analysis (if feasible), is no more than 10%.

5. Based on prior PK data, individual doses may be adjusted, if needed, such that a predicted individual Day 1 AUC (0-24) or Cmax does not exceed 4.9 $\mu\text{g.h/mL}$ or 0.443 $\mu\text{g/mL}$, respectively.

Dosing with food in Part A will be initiated after the exposures achieved with at least two dose levels administered in a fasted state are already known.

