10.3.1. Interim Analysis

No formal interim analyses are planned for this study. However, safety, tolerability, and pharmacokinetic data will be reviewed before each dose escalation in Part A (single dose) and Part B (repeat dose), and prior to the investigation of the food effect.

The relationship between dose and plasma GSK3036656 exposure, and associated variability will be characterized by a power model once data are available from 3 dose levels. Prior to that, prediction of the human exposure at the next dose will be based on population PK modelling (if feasible) or on the assumption of dose–exposure proportionality (i.e., doubling the dose gives an approximate doubling of exposure). If prior PK results show less than proportional increase in exposure with increasing dose, the prediction will be based on the assumption that the fold exposure increase to fold dose increase ratio will be the same with the current dose escalation as it was with the previous one. If prior PK results show more than proportional increase in exposure with dose, subsequent dose escalations will not be higher than 3-fold. The power model will be updated as data become available throughout the study. During dose escalation, and once data is available from 3 doses, a Bayesian predictive probability that an individual will have $AUC(0-24)$ greater than 4.9 $\mu\text{g.h/mL}$ or a C_{max} greater than 0.443 $\mu\text{g/mL}$,

will be calculated for the next dose level and used together with safety and tolerability data to aid the next dose selection.

The Bayesian predictive probability will be based on Whitehead's model [[Whitehead, 2001](#)]:

$$\log(y_{ij}) = \theta_1 + \theta_2 \cdot \log(d_{ij}) + \varepsilon_{ij}$$

where

- y_{ij} is the observed or predicted log-AUC variable (AUC[0-24]) or log-Cmax of the j-th dose d_{ij} administered to the i-th subject
- θ_1, θ_2 are population intercept and slope, respectively.
- ε_{ij} is a random error term, with mean zero and variance σ^2 .

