13. APPENDICES

13.1. Appendix 1: Abbreviations and Trademarks

Abbreviations

μg	Microgram
AE	Adverse Event
Ae	Excretion of unchanged drug
ALT	Alanine aminotransferase (SGPT)
ANOVA	Analysis of Variance
AST	Aspartate aminotransferase (SGOT)
AUC	Area under concentration-time curve
AUC($0-\infty$)	Area under the concentration-time curve from time zero (pre-dose) extrapolated to infinite time
AUC($0-t$)	Area under the concentration-time curve from time zero (pre-dose) to last time of quantifiable concentration within a subject across all treatments
AUC($0-\tau$)	Area under the concentration-time curve from time zero (pre-dose) during a dosage interval
AUC(Ro)	Observed Accumulation Ratio for AUC observed accumulation ratio for AUC
AUC[0-24]	Area under the concentration-time curve from time zero (pre-dose) to 24 hours post dose
BMI	Body mass index
BUN	Blood urea nitrogen
CI	Confidence Interval
CIOMS	Council for International Organizations of Medical Sciences
CL	Clearance
CLR	Renal Clearance
C_{max}	Maximum observed concentration
CONSORT	Consolidated Standards of Reporting Trials
CPK	Creatine phosphokinase
CPMS	Clinical Pharmacology Modelling and Simulation
CPSSO	Clinical Pharmacology Sciences and Study Operations
CRF	Case Report Form
C _T C _T C _T C _T	Trough Concentration (C _T)
DEC	Dose Escalation Committee
DRF	Dose Range Finding
DS-TB	Drug-Sensitive-Tuberculosis
ECG	Electrocardiogram
EDTA	Ethylenediaminetetraacetic acid
FDA	Food and Drug Administration
fe	Fraction of the dose excreted in urine
FRP	Females of Reproductive Potential
FSH	Follicle Stimulating Hormone
FTIH	First Time In Human

GCP	Good Clinical Practice
GCSP	Global Clinical Safety and Pharmacovigilance
GFR	Glomerular Filtration Rate
GLP	Good Laboratory Practice
GSK	GlaxoSmithKline
h	Hour
HBsAg	Hepatitis B surface antigen
hCG	Human Chorionic Gonadotrophin
HED	Human Equivalent Dose
Hep B	Hepatitis B
Hep C	Hepatitis C
Hg	Mercury
Hgb	Haemoglobin
HIV	Human Immunodeficiency Virus
HMR	Hammersmith Medicines Research
HPLC	High Performance Liquid Chromatography
HRT	Hormone Replacement Therapy
IB	Investigator's Brochure
ICF	Informed Consent Form
ICH	International Conference on Harmonisation
IDSL	Integrated Data Standards Library
IEC	Independent Ethics Committee
Ig	Immunoglobulin
INR	International Normalised Ratio
IUD	Intrauterine Device
IUS	Intrauterine Hormone-Releasing System
IVIVE	In vitro in vivo extrapolation
kg	Kilogram
L	Litres
LBF	Liver Blood Flow
LDH	Lactate dehydrogenase

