7.2.1.3. Pharmacokinetic Parameters

7.2.1.3.1. Deriving Pharmacokinetic Parameters

- Refer to [Appendix 4](#): Data Display Standards & Handling Conventions (Section 10.4.3. Reporting Process & Standards).
- Plasma GSK3036656 concentration-time data will be analyzed by non-compartmental methods according to current working practices with WinNonlin 5.2 or higher.
- Non-compartmental analysis will be performed in accordance with GSK PK Guidance document GUI_51487.
- All calculations of non-compartmental parameters will be based on actual sampling times recorded during the study.
- Pharmacokinetic parameters described in [Table 5](#) will be determined from plasma concentration-time data and urine concentration data, as data permits.

Table 5 Derived Pharmacokinetic Parameters

Parameter	Parameter Description
AUC(0-t)	Area under the concentration-time curve from time zero to the time of the last quantifiable concentration (C(t)) will be calculated using the linear trapezoidal rule for each incremental trapezoid and the log trapezoidal rule for each decremental trapezoid.
AUC(0-∞)	Area under the concentration-time curve extrapolated to infinity calculated as: $\text{AUC} = \text{AUC}(0-t) + C(t) / \lambda_z$
AUC(0-24h)	Area under the concentration-time curve from time zero to 24 hours post-dose
AUC(0-τ)	AUC from time zero during a dosing interval of duration “τ”
AUC(Ro)	Observed accumulation ratio (Ro) for AUC will be calculated as follows: $\text{Day 14 AUC}(0-\tau) / \text{Day 1 AUC}(0-\tau)$
Ae	Urinary excretion of unchanged drug
Cmax	Maximum observed blood concentration, determined directly from the concentration-time data.

Parameter	Parameter Description
Ctrough	Pre-dose observed concentration, will be obtained directly from the concentration-time data.
CLr	Renal clearance
Fe	Fraction of the dose excreted in the urine
Lambda_z	The first order rate constant associated with the terminal (log-linear) portion of the concentration-time curve.
Rss	Steady state ratio (Rss) will be calculated as follows: Day 14 AUC(0- τ)/Day 1 AUC(0- ∞)
RCmax	Observed accumulation ratio for Cmax (RCmax) will be calculated as follows: Day 14 Cmax/Day 1 Cmax
tmax	Time to reach Cmax, determined directly from the concentration-time data.
t _{1/2}	Apparent terminal phase half-life will be calculated as: $t_{1/2} = \ln 2 / \text{Lambda}_z$ (NOTE: Lambda_z is the terminal phase rate constant).

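### For a divided Part A dose, the Day 1 AUC(0-24) test can understate the highest 24-hour AUC and so admit a somewhat larger dose than the 30-fold margin allows (minor)

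*Protocol*

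**What the plan says.** The Protocol synopsis and section 4.1 allow a divided dose in Part A: "Dividing the total dose for the treatment (dosing) period into 2 or 3 smaller doses administered within 24 hours may also be done". No spacing is given.

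The purpose of the exposure cap is stated twice. Protocol 4.5 sets the AUC(0-24) limit at 4.9 µg.h/mL and the Cmax limit at 0.443 µg/mL, and introduces them with the words "the maximum individual daily human exposure after single or repeat dose in the study will be limited to". Protocol 6.3 says the study aims to "limit the maximum individual daily plasma AUC(0-24) and Cmax after single or repeat dose" to those values.

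The dose-selection rules are in Protocol 6.3.1. Rule 4 allows at most 10% for "the predicted probability of an individual exceeding a Day 1 plasma AUC (0-24") of 4.9 µg.h/mL, or the Cmax limit. Rule 5 permits individual dose adjustment against the same Day 1 quantities. By contrast, rule 4 for Part B (6.3.2) covers every day of the dosing period.

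Both documents fix the window. Protocol Appendix 1 defines AUC[0-24] as "Area under the concentration-time curve from time zero (pre-dose) to 24 hours post dose", and SAP Table 5 has "Area under the concentration-time curve from time zero to 24 hours post-dose". Neither gives a variant for a divided dose. The only adaptation is footnote 2 to the Part A Time and Events table, which lets assessment times change by file note.

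Criterion 2 in Protocol 5.5 stops escalation if "At least one subject has a plasma AUC (0-24) higher than" 4.9 µg.h/mL, or exceeds the Cmax limit, on any day.

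**The concern.** With one intake, the 24 hours from time zero contain nearly all of the highest 24-hour exposure. With two or three intakes, the later fractions are cut off at 24 h after the first, and the highest 24-hour period starts later. A divided regimen that just passes on Day 1 AUC(0-24) may therefore exceed 4.9 µg.h/mL over its highest 24 hours.

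The cap matters because Protocol 4.6.1 states that the valvular and vascular lesions seen in dogs cannot be monitored in people. Exposure limitation is the main protection, and the subjects are healthy volunteers. The gap would open if a divided regimen were simulated or observed on the literal window and that value were used to accept a larger total dose, to pass criterion 2, or to feed the power model.

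**Working it through.** **The plan's own figure.** 147.0/4.9 = 30.0 and 13.3/0.443 = 30.0. The 30-fold margins in Protocol 4.5 reproduce.

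**Inputs from the documents.** Limits of 4.9 µg.h/mL and 0.443 µg/mL; dog NOAEL AUC 147.0 µg.h/mL; predicted half-life 30 h (range 12 to 72 h, Protocol 4.1).

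**Assumptions.** Linear PK, equal fractions, fractions at 0/12 h or 0/8/16 h, and absorption from instantaneous to ka = 0.5 per h. None of these is in the documents.

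**Formula.** Let F(t) be the share of a fraction's total AUC accrued by time t after intake, with F = 0 before intake. For fractions taken at times d, AUC over [s, s+24] is proportional to the mean of F(s+24−d) − F(s−d). Its maximum over s is compared with its value at s = 0. In one compartment with ke = ln 2/half-life:
- instantaneous: F(t) = 1 − exp(−ke·t)
- oral: F(t) = ke·ka/(ka−ke) × [(1−exp(−ke·t))/ke − (1−exp(−ka·t))/ka]

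**One case by hand** (30 h, 0/12 h, instantaneous). F(12) = 0.2421, F(24) = 0.4257, F(36) = 0.5647.
- AUC(0-24) = (0.4257 + 0.2421)/2 = 0.3339.
- AUC(12-36) = [(0.5647 − 0.2421) + 0.4257]/2 = 0.3741.
- Ratio 1.120. At AUC(0-24) = 4.9, the highest 24-hour AUC is 4.9 × 1.120 = 5.49, and 147/5.49 = 26.8-fold.

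**One compartment, 30 h, instantaneous to ka 0.5:**

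| Regimen | AUC(0-24) | Highest 24 h | Ratio | Highest AUC at the limit | Margin |
|---|---|---|---|---|---|
| Undivided | 0.426-0.398 | 0.426-0.408 | 1.00-1.03 | 4.90-5.03 | 30.0-29.2 |
| 0/12 h | 0.334-0.302 | 0.374-0.369 | 1.12-1.22 | 5.49-5.99 | 26.8-24.5 |
| 0/8/16 h | 0.301-0.268 | 0.363-0.360 | 1.21-1.34 | 5.90-6.58 | 24.9-22.3 |

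Closer spacing (0/4, 0/6 or 0/4/8 h) gives ratios of 1.02-1.15. A 12 h half-life gives 1.00-1.16. A 72 h half-life gives 1.24-1.36 (0/12 h) and 1.36-1.52 (0/8/16 h). With AUC(0-24) at 4.9, Cmax in the divided one-compartment cases is 0.24-0.35 µg/mL, so the Cmax limit does not compensate.

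**Adding a distribution phase.** Two exponentials: terminal half-life 30 h, initial half-life 2-6 h, ka 0.5-2 per h, all assumed.

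| Share of AUC in the initial phase | Ratio, 0/12 h | Ratio, 0/8/16 h |
|---|---|---|
| 0% | 1.14-1.22 | 1.24-1.34 |
| 10% | 1.01-1.12 | 1.09-1.24 |
| 20% | 1.00-1.06 | 1.01-1.18 |
| 30% | 1.00-1.04 | 1.00-1.14 |

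Here Cmax can bind first. For 0/12 h, initial half-life 2 h, ka 2 and a 30% share, Cmax is 0.46 µg/mL when AUC(0-24) is 4.9.

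**Same total dose, split.** Across the half-lives and spacings examined in one compartment, the highest 24-hour AUC is 0.81-1.04 of the undivided AUC(0-24).

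**Total dose admitted, relative to undivided** (30 h, one compartment):
- Literal window: 0.4257/0.3339 = 1.27 to 0.3978/0.3017 = 1.32 (0/12 h); 1.41-1.49 (0/8/16 h).
- Highest window: 0.3978/0.3689 = 1.08 to 0.4257/0.3741 = 1.14; 1.11-1.17.

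**Criterion 2.** If a day means any 24-hour period, it closes the gap after dosing. If it means consecutive blocks, then at 30 h in one compartment AUC(24-48)/AUC(0-24) is 0.85-0.99 for 0/12 h, which is not caught. For 0/8/16 h the ratio is 0.99 with instantaneous input and 1.03-1.16 with ka 0.5-2, which is caught.

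**Power model.** The protocol's outcome "is the observed or predicted log-AUC variable (AUC[0-24]) or log-Cmax of the j-th dose" is regressed on log dose with no regimen term. At 30 h a divided-dose AUC(0-24) enters 22-24% low (0/12 h: 0.3339/0.4257 = 0.784; 0.3017/0.3978 = 0.758) or 29-33% low (0/8/16 h) against the same total dose undivided. Substituting the highest-window AUC still leaves it 7-12% low (0.3689/0.3978 = 0.927; 0.3741/0.4257 = 0.879) or 10-15% low.

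**The case against.** The strongest objection concerns size. The large ratios need one-compartment disposition, and a modest distribution phase removes most of the 0/12 h gap. The documents give some reason to expect one. The PBPK values in Protocol 4.5 (CL 7.2 mL/min/kg, V 3.5 L/kg) imply a one-compartment half-life of 0.693 × 3.5/0.432 = 5.6 h. The lowest clearance with the highest volume (1.1 and 4.5) gives 0.693 × 4.5/0.066 = 47 h. The stated range is 12 to 72 h, and both its ends are longer. This is suggestive only, since the prediction methods may differ, but it stands as a reason not to treat 12-34% as general.

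The routes are also narrow. The simulations in SAP 7.1.3 belong to the section on the first two dose levels. After three doses the SAP tool is the power model, which is conservative for a divided dose until divided-dose data enter it. Rule 4 leaves later PK modelling open, but nothing says it would use the literal window for a split dose. The committee sees at least 48 h of PK before escalating, criterion 2 applies on any day, and the Dose Escalation Charter, which is cited but was not available, may address the point. All of this stands and limits the concern.

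Finally, the cap is itself written as AUC(0-24), matched to a dog AUC(0-24), so daily need not mean a sliding window. That is a fair reading of the wording. But the stated aim is the maximum individual daily exposure, and a window that truncates later fractions does not measure that for a divided dose.

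**Conclusion.** The point holds as a minor gap. For a divided Part A dose, rules 4-5 as written can pass a regimen whose highest 24-hour AUC exceeds 4.9 µg.h/mL. At 30 h and 8-12 h spacing the excess is 12-34% in one compartment (margin about 22- to 27-fold) and 0-24% with 10-30% of AUC in an initial phase. It depends on an optional split, wide spacing, and use of the literal window to accept a larger dose.

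Three stronger readings are not supported. A reader might infer that splitting a dose raises exposure; for a fixed total dose it does not materially do so. A reader might take 22-fold as the margin the study will have; that is the low end of the 30 h one-compartment results under assumed spacing, and it is still a large margin. A reader might conclude that nothing catches the excess; criterion 2 may do so, depending on how a day is read, but only after subjects have been dosed.

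**What to change.** In Protocol 6.3.1 rules 4-5 and in 5.5 criterion 2, add: *for a divided Part A dose, the AUC compared with 4.9 µg.h/mL, predicted or observed, is the largest AUC over any 24-hour window.* The limits do not change.

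Use the existing file-note provision to time PK samples after each fraction, because nothing is scheduled between 15 and 24 h. In one compartment at 30 h with ka 0.5-2, the scheduled times alone would understate the highest 24-hour AUC by 2-3% (0/12 h) or 4-7% (0/8/16 h). Three added draws bring this within 2%. At an assumed 2-5 mL each, that is 6-15 mL of the 500 mL limit.

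Do not pool divided-dose and undivided AUCs in the power model without a regimen term. Changing the window alone leaves the divided values about 7-15% low.

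The cost is one sentence in each section, a few lines of code and a few draws. The allowable divided dose also falls. At 30 h in one compartment it drops by 11-18% (1 − 1/1.120 to 1 − 1/1.223) for 0/12 h, or 17-26% (1 − 1/1.205 to 1 − 1/1.344) for 0/8/16 h. It still stays above the undivided dose.
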